A patient who remains in the study for the first two treatment periods or for all four treatment periods will receive a balanced exposure to treatments randomized to receive. If patients discontinue treatment prior to completing the entire 24 weeks of study, all their data (including weekly assessments) from their time in the study will be used in the analyses. Because the main analysis is based on maximum likelihood estimation using a mixed-effects multi-period crossover model, the inferences will be unbiased under missing at random assumptions. No imputation of missing data is planned for this study, unless intensive investigations indicate that reliable and valid data imputation is possible, in which case multiple imputation will be performed and the analysis of the imputed data sets will serve as a sensitivity check of the results from the primary analysis based on the mixed-effects models (van Buuren et al, 2011).

All analyses will adjust for age, sex, K-L grade, and site.

All hypothesis tests will be two-sided using 5% significance level, and *p*-values unadjusted for multiple testing will be reported. The justification for this decision is that this is a Phase II investigation and all assessed outcomes are of specific and unique interest. Much more important than testing hypotheses is the efficient estimation of all quantities of interest, and this will be carried out throughout the analyses. Point estimates, 95% confidence intervals and standardized effect sizes (e.g., Cohen's *d*) will be reported for all estimated effects, regardless of whether the null hypotheses were rejected or not.

K.2. Hypothesis testing

Aim 1: Assess the safety of CNTX-6970 (300mg BID).

There will be no formal hypothesis testing under Primary Study Aim 1. All AEs and SAEs observed during different treatment periods will be summarized based on severity and relation to the active treatment (CNTX-6970 300mg BID). The reports will include tabulation of the AEs and SAEs by period, block, and treatment; point estimates and 95% CIs will be reported. Similarly, we will summarize relevant laboratory measures (see Section F.2.1) with appropriate estimates.

Aim 2: Assess the efficacy of CNTX-6970 (300mg BID) in comparison to placebo with respect to the primary outcome measure for pain due to osteoarthritis of the knee - WOMAC Part A.

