the relationship of the between-subject variability to the within-subject variability. In general, the between-subject variability is larger than the within-subject variability, but we investigated a range of Between/Within (B/W) variance ratios (5/1, 2/1). With a total sample size of $n=55$, there will be more than adequate power for the study using a two-sided Type I error rate of $\alpha=0.05$. A power analysis was conducted with $n=50$ and the power to detect an effect size (for an active treatment vs. placebo) of Cohen's $d=0.35$ is approximately 95% when the ratio B/W=2/1. Assuming a 15% early termination rate during each of the 4 periods will yield a sample size of $n=26$ with complete observations at all treatment periods for this simulation. If we conservatively assume that only subjects with complete data will be analyzed, the corresponding power with $n=26$ is approximately 81%. Because we will use all available data from all enrolled subjects in the analysis, the actual power in the case of 15% early termination rate per treatment period will be larger than 81%, and anywhere between 81% and 95%. If the ratio B/W is larger than 2, say B/W=3, 4 or 5, the power for detecting the treatment effects is much larger. For example, with only 26 patients, if B/W=5, the power to detect an effect of magnitude Cohen's $d=0.35$ is 0.96. Note that the reported test-retest reliability of the WOMAC-A measure is 0.86, which corresponds to a B/W=7.

[figure not shown]

Figure 2: Power versus Cohen's d effect size. B/W indicates the ratio of between-subject to within-subject variance of the WOMAC-A measure. Assuming that only data from completers will be used in the analysis gives a lower bound of the power that can be achieved for the given range of effect sizes.

■ PUBLICATION POLICY

See EPPIC-Net Publication Policy.

■ REFERENCES

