The following are secondary physiological outcomes related to pain and potential exploratory biomarkers for pain and treatment response.

- Staircase-evoked pain assessment. This procedure consists of stepping fully up and down onto a 20 cm high platform with both feet a total of 24 times. The lead leg is alternated between each up/down cycle. Subjects are instructed to use their normal gait for completing this task and are encouraged to complete the task despite increasing pain, without stopping if possible. The procedure is timed, and current knee pain intensity on a 0-10 Numeric Rating Scale (NRS) is assessed immediately before and following the procedure while the subject is in a seated, resting position. This staircase-evoked pain assessment has been well tolerated in multiple studies of knee OA participants to date, and the standardized effect size for anti-inflammatory treatments was shown to be considerably higher with the staircase measure than with other measures such as pain intensity ratings (Treister *et al.*, 2019).
- Temporal profile of OA pain will be assessed using the NRS (integer scale from 0-10) at the end of the day for the first seven days following the Screening visit in order to obtain a measure of pain variability **which will be used to screen out individuals with high variability (SD > 1.2) in their pain.** Additionally, after Baseline, the NRS will be completed daily for the seven days immediately preceding all study visits.
- Serum levels of cytokines and chemokines. A specific list is provided in the Appendix of the protocol.
- Monocyte chemoattractant serum protein-1(MCP-1)/CCR-2 receptor binding inhibition by CNTX-6970. This test provides as a single score, expressed as a percentage, 0-100%, with higher scores indicating more binding inhibition.
- Monocyte chemoattractant protein-1 (MCP-1)/CCR-2 receptor binding inhibition by CNTX-6970 in synovial fluid.
- Synovial fluid levels of cytokines and chemokines (a specific list is provided in Appendix of the protocol), assessed at the end of the first treatment period (week 6) which will allow a comparison of subjects treated with CNTX-6970 300 mg BID to placebo-treated subjects.

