## 5.3 Randomization and Blinding

For entry into the study and randomization, all eligibility criteria MUST be met (i.e., all inclusion criteria and no exclusion criteria specified in the protocol). Patients who meet inclusion/exclusion criteria at the Baseline Visit (day 0) will be randomized. After documentation of written informed consent and the screening period, clinical sites will confirm eligibility and complete randomization by accessing the Almac's centralized web-based system for randomization and drug management - the Interactive Web Response System (IXRS). Subjects will be randomized equally between treatment sequences shown in Figure 1: Drug:Placebo:Placebo:Drug or Placebo:Drug:Drug:Placebo. A standard block randomization will be used, stratifying by K-L grade (stratum 1 K-L grade 1 or 2, and stratum 2 K-L grade 3 or 4) to achieve balance on randomization sequences. The randomization will be implemented by the IXRS vendor in consultation with the study statisticians. After Randomization, drug will be dispensed.

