## 6 Sample Size

The sample size for this study was determined based on the primary efficacy aim to detect clinically meaningful and realistic effects of CNTX-6970 (300 mg BID) compared to placebo in the multi-period crossover

design model. Power was computed for effect sizes ranging from 0.25 to 0.50 using Monte Carlo simulation. Data were simulated from multi-period crossover models with block, period, and carryover effects, and varying within and between subject variability.

Although carryover effects can be efficiently isolated and estimated in the analysis stage by using the mixed-effects models proposed in Section 7, power for the primary hypothesis was computed using only WOMAC-A assessed during the last 2 of 6 weeks per treatment period to minimize carryover effects. The power of the test depends on the relationship of the between-subject variability to the within-subject variability. In general, the between-subject variability is larger than the within-subject variability, but a range of Between/Within (B/W) variance ratios (5/1, 2/1) were investigated. With a sample size of  $n = 55$  per arm, using a two-sided Type I error rate of  $\alpha = 0.05$ , the power to detect an effect size (for the active treatment vs. placebo) of Cohen's  $d = 0.35$  exceeds 95% when the ratio  $B/W = 2/1$ .

Assuming a 15% early termination (e.g., dropout) rate during each of the 4 periods will yield a sample size of approximately  $n = 29$  with complete observations at all treatment periods. If we conservatively assume that only subjects with complete data will be analyzed, the corresponding power with  $n = 29$  exceeds 80% when the ratio  $B/W = 2/1$  with an effect size as low as 0.30. Figure 2 shows the results of a simulation study to evaluate the power of this design. Because we will use all available data from all enrolled subjects in the analysis, the actual power in the case of 15% early termination per treatment period will be larger than what Figure 2 shows. If the ratio B/W is larger than 2, say B/W=3, 4 or 5, the power for detecting the treatment effects is much larger. For example, with only 29 participants, if B/W=5, the power to detect an effect of magnitude Cohen's  $d = 0.35$  exceeds 0.95. Note that the reported test-retest reliability of the WOMAC-A measure is 0.86, which corresponds to a  $B/W = 7$ .

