**Aim 5:** The hypotheses under aim 5 are for staircase-evoked pain assessment, serum and synovial fluid levels of chemokines and cytokines; and synovial monocyte chemoattractant protein-1/CCR-2 receptor binding inhibition in blood and synovial fluid. Hypotheses for Staircase-Evoked Pain Assessment, will be tested with the same approaches as for testing the hypotheses under Aim 3 which can accommodate outcomes on participants measured at more than one occasion. For synovial fluid, which is only collected once, the hypothesis testing will use the same approach as for hypotheses under Aim 4 - we will model the week 6 assessment of measures as functions of treatment in the first period, adjusting for sex, age and K-L Grade. The analysis for serum chemokines/cytokines will be more complicated since these measures are obtained at multiple occasions and we want to assess if their impact on pain differs due to treatment in this multi-crossover study. Analytical methods for this complex type of mediation analysis still need to be developed. We will evaluate the impact of the treatment sequence on the change in the WOMAC-A from baseline to V9, modeling serum and synovial fluid levels of chemokines and cytokines as potential mediators of treatment effect by investigating a generalization of the  $2 \times 2$  crossover mediation modeling approaches introduced by (Josephy *et al.*, 2015) and generalized to this multi-crossover trial design.

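### The Aim 5 mediation analysis is defined as a between-sequence comparison of one WOMAC-A change score, and it ties week-6 synovial levels to a week-24 outcome

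*SAP*

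**What the plan says.** SAP 9.2 handles the Aim 5 measures in three ways. Staircase-evoked pain goes into the Aim 3 crossover model. Synovial levels, collected once, are compared directly at week 6 by first-period treatment. For serum markers the SAP says that suitable mediation methods do not yet exist. It then fixes the exposure and outcome, "We will evaluate the impact of the treatment sequence on the change in the WOMAC-A from baseline to V9", and continues with "modeling serum and synovial fluid levels of chemokines and cytokines as potential mediators of treatment effect", to be done by extending a 2×2 crossover mediation approach. The SAP reference list shows that approach to be one for within-subject mediation in AB/BA designs.

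The related facts are:

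- SAP 5.3: patients are allocated equally to "Drug:Placebo:Placebo:Drug or Placebo:Drug:Drug:Placebo".
- SAP 4.4.3: synovial levels are "assessed at the end of the first treatment period (week 6) which will allow a comparison of subjects treated with CNTX-6970 300 mg BID".
- Protocol F.2.2: serum is drawn at baseline and weeks 6, 12, 18 and 24/ET. Sites and participants may each decline the synovial tap.
- Protocol F.1.1: WOMAC-A is weekly after screening, and every third assessment falls at a clinic visit.
- SAP 9.1: carryover is expected to have disappeared after the first four weeks of a period.

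Neither document gives a power figure for the mediation analysis.

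**The concern.** A four-period crossover earns its efficiency from drug-minus-placebo differences within the same patient. An outcome with one baseline-to-V9 change per patient, compared by sequence, contains no such difference. The total effect to be split into direct and indirect parts would then be estimated far less precisely than the collected data allow, and a report of no mediation would tell the reader little.

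The synovial part has a further difficulty. A marker level at the end of period 1 is asked to explain pain at the end of period 4, after the patient has crossed to the other treatment and back. If carryover is gone within four weeks, as the plan expects, a period-1 marker response is not a route by which period-4 treatment could act on week-24 pain.

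**Working it through.** **Inputs.** Two-sided 5% (Protocol K.1: "All hypothesis tests will be two-sided using 5% significance level"). d = 0.35 "when the ratio B/W=2/1" (Protocol K.4). SAP 6 says that "a range of Between/Within (B/W) variance ratios (5/1, 2/1) were investigated", and that the "reported test-retest reliability of the WOMAC-A measure is 0.86", which it equates to B/W = 7. (The usual conversion, 0.86/0.14, gives 6.1. I keep 7, which favours the change score.) Completers: 55 × 0.85⁴ = 28.7, the SAP's 29. Assumption: d is in total-SD units, so the within-patient variance is W = 1/(1 + B/W).

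**What the stated contrast estimates.** Write D for drug and P for placebo. Under SAP model (1), the week-24 mean is β0 + γ2 + δ2 + β1 in DPPD and β0 + γ2 + δ2 in PDDP. Baseline precedes treatment. The difference in mean change between sequences is therefore β1, taken from period 4 only and between patients.

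**Variances, one value per period, no carryover term.**

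- Change score by sequence: each change has variance 2W. With n/2 patients per sequence, the variance of the difference is 2W(2/n + 2/n) = 8W/n.
- Within-patient: the mean of two drug periods minus the mean of two placebo periods has variance W/2 + W/2 = W per patient, so W/n overall. Block and period effects cancel in both sequences.
- Ratio: 8, at every n and B/W.

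Power = Φ(d/SE − 1.96).

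**Check against the plan's own figures.** For n = 29, B/W = 2, d = 0.30: SE = √(0.3333/29) = 0.107 and power = 79.9%, where SAP 6 says above 80%. For n = 55, B/W = 2, d = 0.35: 99.4% (SAP: above 95%). For n = 29, B/W = 5, d = 0.35: 99.6% (SAP: above 95%). The formula is more optimistic than the simulations in Protocol K.4. It gives 99.0%, 87.1% and 99.2% where K.4 has about 95% (n = 50), about 81% (n = 26) and 96% (n = 26, B/W = 5). A version with a carryover term, two weekly values per period and an assumed AR(1) of 0.25 comes closer, at 97.0%, 79.0% and 97.4%.

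**Result at d = 0.35.** For n = 29 and B/W = 2, the change-score SE is √(8 × 0.3333/29) = 0.303, so power = Φ(1.154 − 1.96) = 21%. The within-patient SE is 0.107, so power = Φ(3.265 − 1.96) = 90%.

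| n | B/W | Change score by sequence | Within-patient |
|---|---|---|---|
| 29 | 2 | 21% | 90% |
| 29 | 5 | 37% | 99.6% |
| 29 | 7 | 47% | about 100% |
| 55 | 2 | 36% | 99.4% |
| 55 | 5 | 61% | about 100% |
| 55 | 7 | 74% | about 100% |

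**Sensitivity at n = 29, B/W = 2.** Adjusting for baseline instead of taking a change raises 21% to 24%. Adding the model (2) carryover term doubles the within-patient variance to 2W/n. Power is then Φ(0.35/√(0.6667/29) − 1.96) = 64%, and the variance ratio falls to 4. With two values per period and AR(1) 0.25 the figure is about 83%.

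**Timing of mediator and outcome.** Serum is available at weeks 6, 12, 18 and 24, each with a WOMAC-A at the same visit. Synovial fluid is available at week 6 only. From week 6 to week 24, DPPD patients go to placebo at week 6 and back to drug at week 18, and PDDP patients do the reverse. That is exactly two switches over 18 weeks.

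**The case against.** The strongest reply is that this part of the SAP is openly unfinished. No equation is given, the same sentence points to a within-subject method and promises to extend it to this design, and SAP 7 makes secondary analyses depend on sufficient data. This stands in part. A reader might infer that the SAP has settled on discarding all within-patient information, and the text does not establish that. However, the exposure and outcome are the parts it does specify, and they do not fit the method it cites.

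Four other stronger readings are tempting but not supported.

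- That the mediation analysis has 21% power. That figure is for the total effect at the least favourable n and B/W, and Aim 2 tests the total effect properly with all four periods. No mediator effect, mediator variance or synovial sample size is given, so power for an indirect effect cannot be calculated.
- That week-6 synovial levels and week-24 pain come from opposite treatments. SAP 9.2 itself notes that first- and last-period treatment coincide. The problem is the crossover in between and the 18-week gap.
- That the timing objection covers serum. It does not.
- That early-termination values will enter as V9. Protocol F.1.14 does combine Week 24 and Early Termination under Visit 9, but SAP 9.2 identifies V9 with week 24 when describing the PGIC analysis. One clarifying line is enough.

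It is also fair to say that the direct synovial test already pairs week-6 levels with first-period treatment. Only the mediation sentence departs from that pairing.

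**Conclusion.** The point holds as a fault in how the mediation exposure, outcome and synovial mediator are defined. It goes beyond missing detail: followed as written, the text gives a between-patient period-4 contrast and links a period-1 synovial level to a period-4 outcome. For the total effect, the stated contrast has eight times the variance of the within-patient contrast, or four times if a carryover term is fitted with one value per period. Power over the documents' own n and B/W is about 21–74% against 90–100%, and the within-patient figure at n = 29, B/W = 2 drops to about 64–83% with a carryover term. These figures assume d = 0.35 in total-SD units, an unadjusted change score and, apart from the 83%, one value per period. They say nothing numerical about the mediated effect. The primary analysis is not affected.

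**What to change.** In SAP 9.2, Aim 5, replace the stated exposure and outcome along these lines:

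- *Serum.* Estimate the effect of period treatment on WOMAC-A at the end-of-period visit (weeks 6, 12, 18 and 24), with the serum level at the same visit as mediator. Use within-patient contrasts with block and period terms, and add the model (2) carryover term as a sensitivity analysis. Using the visit value alone avoids setting a week-5 outcome before a week-6 mediator.
- *Synovial fluid.* Use it as a mediator only for week-6 WOMAC-A by period-1 treatment. Report this as a small exploratory between-patient analysis, since sampling is optional.
- *Interpretation.* State that mediator and outcome are contemporaneous, so the results are associational. At week 6 the WOMAC-A is in fact completed before the tap (Protocol F.1.8).
- *Early termination.* Assign any such value to the period and treatment in which it was collected, and do not count it as week 24.

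The cost is a SAP text change, best made before the sequence codes are released. No new data are needed. The model has more rows per patient, and the synovial analysis is limited to period 1. The split into direct and indirect effects still has to be written out, as the SAP already acknowledges.

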### 9.3 Exploratory Analyses

**Aim 6.** If CNTX-6970 is more effective than placebo, we will evaluate the following characteristics of its effect: (a) onset of action; (b) carryover effect after treatment discontinuation. We will study the change of symptoms over time using a time trend in our statistical models within each of the 6-week treatment periods to model the weekly WOMAC-A measure. Under this aim, the interest is not in hypothesis testing, but

rather in understanding the progression and magnitude of onset of action and the carryover effects of the CNTX-6970 compound. This approach will allow an elucidation of the nature of action of the compound. Specifically, we will study the change of symptoms over time using the following mixed-effect multi-period crossover model that incorporates a time trend within each of the 6-week treatment periods to model the weekly WOMAC-A measure:

$$y_{i(s)jkm} = \beta_0 + \gamma_j + \delta_k + \beta_1 X_{i(s)jk} + \alpha_0 t_{i(s)jk} + \alpha_1 X_{i(s)jkt_{ijkm}} + \lambda_{0.drg} Z_{i(s)jk,drg} + \lambda_{1.drg} Z_{i(s)jk,drg} t_{i(s)jk} + \beta'_2 \mathbf{w}_{i(s)} + b_s + b_{i(s)m} + \epsilon_{i(s)m}, \quad (3)$$

where  $t_{i(s)jkm}$  is the patient's  $i(s)$  time measure (at site  $s$ ) within block  $j$  and period  $k$  at the  $m$ th assessment and the common notations are defined as in equation (1). The coefficient  $\alpha_0$  is the slope for change of symptoms during a placebo treatment period, when that period was preceded by none or a placebo treatment period;  $\alpha_1$  (the slope of the change of symptoms during an active treatment period) is a measure of the speed of the onset of action of the active drug; counting week 6 of the previous period as the baseline for the next period,  $\lambda_{0.drg}$  is the active treatment's carryover effect at the start of a placebo treatment period that follows an active treatment period;  $\lambda_{1.drg}$  is the difference in the slopes of treatment change during placebo treatment between two conditions: when the placebo treatment period is preceded by active treatment versus when the placebo treatment period is preceded by no or placebo treatment. Thus  $\lambda_{1.drg}$  will measure the speed of carryover effect disappearance after the active treatment is discontinued.

**Aim 7.** The biomarker-related objectives are to identify physiological and behavioral measures that are related to established indices of pain from OA of the knee (e.g., WOMAC-A), as well as general pain-related measures (e.g., depression, anxiety, sleep). All results from these discovery analyses will be reported as exploratory and will be subject to independent validation. The interpretation of the results will also be in the context of all analyses that were performed and will emphasize the discovery nature of the work. Statisticians on the study team have developed and published methods for analysis of complex multimodal data for developing optimal treatment decision rules (e.g., Petkova *et al.*, 2016; Ciarleglio *et al.*, 2018; Park *et al.*, 2017, 2020a,b) which is a primary objective of precision medicine. Although this previous work has been primarily motivated by mental health research (e.g., depression), these methodologies are very general and are applicable to pain and other medical conditions. As necessary, new methodologies will be developed for the analysis of the data, collected simultaneously over several weeks. The results of these investigations are expected to be features (for example, the variability of pain across days as measured by daily NRS scores) or combinations of features that constitute biosignatures for specific response to CNTX-6970 and placebo response.

**Aim 8:** This aim will explore sociodemographic and clinical predictors of response to CNTX-6970 by examining the relationship between treatment with CNTX-6970 and placebo, and sociodemographic and clinical covariates. No hypotheses will be tested under this aim. Rather various research questions will be addressed, such as:

Question 1. Do women show a greater reduction in pain ratings following CNTX-6970 compared to placebo, relative to men?

Question 2. Do patients with high levels of psychological distress show a greater reduction of pain with CNTX-6970, relative to patients who do not have high levels of psychological distress?

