### 9.1 Primary Efficacy Analysis

For the efficacy Aim 2, data from the WOMAC Part A (WOMAC-A) assessed only in the last two weeks of each 6-weeks treatment period will be used for this primary analysis in order to avoid any carryover effects, which are expected to vanish after 4 weeks. Hypothesis 1 in Section 4 will be tested using the following random-effects multi-period crossover model that employs block and period effects to compare the active treatment to placebo (Zucker *et al.*, 1997; Chen and Chen, 2014). Specifically, the model is:

$$y_{i(s)jkm} = \beta_0 + \gamma_j + \delta_k + \beta_1 X_{i(s)jk} + \beta_2' \mathbf{w}_{i(s)} + b_s + b_{i(s)} + \epsilon_{i(s)m}, \quad (1)$$

where  $i(s)$  is the index for patient  $i$  at site  $s$ ;  $\beta_0$  is the intercept;  $j$  is the index for block,  $j = 1, 2$  and  $\gamma_j$  is the block effect;  $k$  is the index for period,  $k = 1, 2$ , and  $\delta_k$  is the period effect;  $m$  is the measurement time;  $y_{i(s)jkm}$  is the primary outcome for subject  $i(s)$ , block  $j$ , period  $k$ , time  $m$ ;  $\beta_1$  represents the treatment effect, and  $X_{i(s)jk}$  is an indicator for active treatment ( $X_{i(s)jk} = 1$ ) or placebo ( $X_{i(s)jk} = 0$ ) for patient  $i(s)$ , in block  $j$ , during period  $k$ ;  $\mathbf{w}_{i(s)}$  is a vector of baseline characteristics (e.g., age, sex, K-L grade indicator) for patient  $i(s)$  and  $\beta_2$  is a vector of coefficients for those baseline characteristics;  $b_s \sim N(0, \sigma_{site}^2)$  is a random site effect and  $b_{i(s)} \sim N(0, \sigma_b^2)$  is a subject-level random effect (nested within site);  $\epsilon_{i(s),m}$  is a random error with an  $AR(1)$  structure:  $\epsilon_{i(s),m} = \phi \epsilon_{i(s),m-1} + u_{i(s)m}$ , with  $u_{i(s)m} \sim N(0, \sigma_u^2)$ . The subject-level random effects will model the repeated measures within subjects. The block and period effect terms will accommodate changes in mean pain scores across blocks and periods of the design.

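### In Aim 6, α1 of model (3) is the active-minus-placebo slope difference, not the active-period slope, and read alone it can make a rapid onset look slow

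*SAP*

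**What the plan says.** SAP 9.3 (Aim 6) proposes model (3), which "incorporates a time trend within each of the 6-week treatment periods to model the weekly WOMAC-A measure". Its treatment and time terms are β1·X + α0·t + α1·X·t, together with two carryover terms, λ0·Z and λ1·Z·t.

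The SAP interprets the terms as follows:

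- X "is an indicator for active treatment", coded 1, with placebo coded 0 (SAP 9.1).
- β1 "represents the treatment effect" (SAP 9.1, carried over to model (3)).
- For α0 the text reads "is the slope for change of symptoms during a placebo treatment period", restricted to placebo periods that do not follow an active one.
- α1 is glossed as "the slope of the change of symptoms during an active treatment period) is a measure of the speed of the onset of action".
- λ1 "is the difference in the slopes of treatment change during placebo treatment between two conditions".

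The SAP counts week 6 of the preceding period as the baseline of the next when it defines the carryover terms. Aim 6 is exploratory, applies only if the drug beats placebo, and involves no hypothesis test. It asks about onset of action and carryover. No numerical value or assumed onset curve is given.

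**The concern.** There are two separate problems with the sentence about α1. First, it names the wrong quantity: a coefficient on X·t that sits beside a common α0·t is a difference in slopes. Second, a slope is a poor stand-in for speed when the model also lets the curves be apart at t = 0. An effect that arrives before the first assessment has no slope left to show.

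If the sentence is followed literally, the report would give the slope difference as the active-period slope. It might also describe a quick-acting drug as slow in onset because α1 is small. Protocol D.1 justifies the crossover design partly by the drug's rapid onset and short half-life, so this is the region in which the trial expects to be.

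**Working it through.** **Inputs.** X coding and β1 come from SAP 9.1; α0, α1, λ1 and the linear trend from SAP 9.3; the sequences Drug:Placebo:Placebo:Drug and Placebo:Drug:Drug:Placebo from SAP 5.3; weekly WOMAC-A from the notes to the protocol's Schedule of Events. The t in the α1 term is read as a multiplier, the only reading under which α1 is a slope. The plan has no figure of its own to reproduce here.

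**Step 1: the label.** Differentiate model (3) with respect to t, with Z = 0:

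- placebo (X = 0): slope = α0
- active (X = 1): slope = α0 + α1
- difference: α1

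For illustration, α0 = −0.5 and α1 = −1.0 points per week give an active slope of −1.5, not −1.0. This step needs no assumption. The SAP treats the parallel interaction λ1 correctly, as a difference in slopes.

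**Step 2: where an early effect goes.** With Z = 0 the modelled active–placebo contrast at time t is β1 + α1·t. If the full effect E is present at every assessment, then β1 = E and α1 = 0. The fastest possible onset scores zero on the SAP's speed measure.

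**Step 3: size over a range of onset speeds.** Assume a drug effect of E·(1 − 2^(−t/h)), where h is the onset half-time. This curve is an assumption and is not in the documents. The least-squares slope is Σ(t − t̄)y / Σ(t − t̄)², with denominator 17.5 for t = 1..6 and 28 for t = 0..6. Size of α1 per week, as a share of E:

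| h (weeks) | share of E reached at week 1 | t = 1..6 | t = 0..6 |
|---|---|---|---|
| 0.1 | 0.999 | 0.0001 | 0.107 |
| 0.5 | 0.750 | 0.041 | 0.127 |
| 1 | 0.500 | 0.090 | 0.146 |
| 2 | 0.293 | 0.114 | 0.141 |
| 4 | 0.159 | 0.097 | 0.107 |
| 6 | 0.109 | 0.078 | 0.083 |

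Hand check for h = 0.5, t = 1..6: [2.5(0.9998 − 0.7500) + 1.5(0.9990 − 0.9375) + 0.5(0.9961 − 0.9844)] / 17.5 = 0.7225 / 17.5 = 0.041. For an effect complete by week 1 on t = 0..6: (−2 − 1 + 0 + 1 + 2 + 3) / 28 = 3/28 = 0.107.

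The peak lies near h = 2.04 weeks on the 1–6 grid and near h = 1.29 weeks (0.148) on the 0–6 grid. On the 0–6 grid, half-times of 0.1 and 4 weeks give the same α1.

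**Step 4: the same check inside model (3).** The block, period, treatment, time and carryover terms were fitted without noise to both sequences, with a random subject intercept, AR(1) correlation of 0 or 0.5, and a between/residual variance ratio of 2. Baseline covariates and site were left out. With E = 5 points, weeks 1–6, no autocorrelation and no carryover:

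| h (weeks) | β1 | α1 | β1 + α1 (fitted, week 1) | true week-1 effect |
|---|---|---|---|---|
| 0.1 | −5.00 | −0.001 | −5.00 | −5.00 |
| 0.5 | −4.00 | −0.206 | −4.21 | −3.75 |
| 1 | −2.61 | −0.449 | −3.06 | −2.50 |
| 2 | −1.25 | −0.569 | −1.82 | −1.46 |
| 6 | −0.23 | −0.390 | −0.62 | −0.55 |

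All 16 combinations of time grid, autocorrelation, coding of Z and carryover gave a non-monotone α1. Among the half-times fitted, the largest α1 was always at 1, 2 or 3 weeks. The fitted week-1 contrast in the table is monotone in speed, though the straight line overstates the week-1 effect at intermediate speeds (3.06 against 2.50 at h = 1).

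**The case against.** The strongest defence is that model (3) does carry early onset, because β1 is in it. The contrast β1 + α1·t orders onset speeds correctly at week 1 in the table above. This stands: a reader might infer that a straight line cannot measure onset at all, and that is too strong. What remains is that the SAP names α1 as the onset measure, names no other, and does not say that the weekly contrast will be reported.

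It can also be said that α1 is the more useful coefficient, since it removes placebo drift, and that only its label is wrong. That is fair for the first problem. It does not answer the second.

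A reader might infer that the plan would rank drugs or doses in the wrong order. The documents do not support this. One dose is compared with placebo, and Protocol C.4 gives the two discontinued arms summary statistics for efficacy. Nor does the slowest onset always get the largest slope: that holds for a strictly linear build-up over six weeks (1/6 = 0.167E per week), whereas a 6-week half-time gets the smallest value on the 0–6 grid. The slow exponential curves also mix speed with effect attained, since h = 6 reaches only half of E by week 6.

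Finally, Aim 6 is exploratory, untested and conditional on efficacy. That limits the consequence but does not make the sentence correct.

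**Conclusion.** The point holds in a limited form. The label on α1 is wrong by algebra, with no assumption needed. That α1 alone is an unreliable measure of onset speed follows from β1 being in the model. How badly it misleads depends on an assumed onset curve that levels off and on the time origin. On weeks 1–6, α1 falls to practically zero for a very fast onset. With t = 0 at the previous week 6, it falls only from a peak of 0.148E to 0.107E per week. If improvement were truly linear over all six weeks with no gap at t = 0, α1 would order speed correctly.

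The practical risk is that a small α1 is read as slow onset. Protocol K.2 gives a mean half-life of 15.8 to 16.6 hours, which divided by 168 hours is about 0.094 to 0.099 week. If pain relief set in at that rate, which is an assumption, α1 on weeks 1–6 would be close to zero. The primary analysis uses model (1) on the last two weeks of each period and is not touched.

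**What to change.** In SAP 9.3, Aim 6:

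1. Define α1 as the active-minus-placebo difference in slopes, and report α0 + α1 (Z = 0) as the active-period slope.
2. Drop the statement that α1 alone measures speed of onset. Describe onset by β1 + α1·t at each of weeks 1 to 6, with 95% CIs from Var(β1) + t²·Var(α1) + 2t·Cov(β1, α1).
3. State the time origin explicitly, since the size of α1 depends on it.
4. Keep model (3), because λ1 needs linear time to describe how fast carryover fades. Add a supportive fit with week (1–6) as a factor crossed with treatment, and report the weekly drug–placebo differences with 95% CIs. This avoids the distortion that the straight line causes at intermediate onset speeds.

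The cost is a few lines of SAP text and a few more model terms, with wider weekly intervals, in an exploratory aim. No new data are needed, as WOMAC-A is already weekly. Protocol K.3 mentions only a time trend and names no coefficient, so the change can stay within the SAP. It is best made before unblinding, so that the description of onset is not chosen from the data.
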